### 18.2 Analysis

An overall summary will be presented as the number of participants within each of the event type categories described in the sub-sections below, including the incidence of TEAEs by SOC and preferred term, unless otherwise specified. Both number of participants, number of mentions (i.e., events) and percentage will be provided.

All TEAEs will be summarized by treatment sequence and period of event as follows:

- All AEs,
- Grade  $\geq 3$  AEs
- AEs related to study treatment, including related Grade  $\geq 3$  AEs,
- All adverse drug reactions, and
- SAEs

All AEs will be listed by participant, along with information regarding onset, duration, relationship, and severity to study treatment, action taken with study treatment, treatment of event, and outcome as captured in the EDC.

### 18.2.1 Incidence of TEAEs

The incidence of all TEAEs by SOC and preferred term and severity will be presented by treatment of event.

### 18.2.2 TEAEs by severity

The Investigator will use the National Cancer Institute (NCI) Common Terminology Criteria for Adverse Events (CTCAE) version 5.0 to describe the severity of AEs. AEs not listed in the CTCAE will be graded as follows:

- **Grade 1:** Mild; asymptomatic or mild symptoms; clinical or diagnostic observations only; intervention not indicated.
- **Grade 2:** Moderate; minimal, local, or non-invasive intervention indicated; limiting age appropriate instrumental activities of daily living (ADL). ADL refers to preparing meals, shopping for groceries or clothes, using the telephone, managing money, etc.
- **Grade 3:** Severe or medically significant but not immediately life-threatening; hospitalization or prolongation of hospitalization indicated; disabling; limiting self-care ADL. Self-care ADL refers to bathing, dressing & undressing, feeding self, using the toilet, taking medications, and not bedridden.
- **Grade 4:** Life-threatening consequences; urgent intervention indicated.
- **Grade 5:** Death related to the AE.

The incidence of all TEAEs will be presented by SOC, preferred term and severity for each treatment of event.

### 18.2.3 Drug-related TEAEs

Classification of Adverse Events by relationship to study treatment:

- **NOT RELATED:** There is not a reasonable possibility that the administration of the study intervention caused the event, there is no temporal relationship between the study intervention and event onset, or an alternate etiology has been established.
- **RELATED:** The AE is known to occur with the study intervention, there is a reasonable possibility that the study intervention caused the AE, or there is a temporal relationship between the study intervention and event. Reasonable possibility means that there is evidence to suggest a causal relationship between the study intervention and the AE.

The incidence of all drug-related TEAEs will be presented by SOC and preferred term for each treatment of event. “*Treatment of event*” will be derived as the last treatment exposed to prior to the onset of the AE.

**18.2.4 Serious TEAEs**

Any untoward medical occurrence, in the view of the Investigator or Sponsor, that:

- Results in death
- Is life-threatening: An AE is life threatening if the participant was at immediate risk of death from the event as it occurred (i.e., it does not include a reaction that might have caused death if it had occurred in a more serious form).
- Requires or prolongs inpatient hospitalization: A hospitalization is defined as  $\geq$  24 hours in hospital or overnight stay. Complications occurring during hospitalization are AEs and SAEs if they cause prolongation of the current hospitalization. Hospitalization for elective treatment of preexisting, non-worsening conditions is not, however, considered an AE. The details of such hospitalizations must be recorded in the medical history/procedures or physical examination page of the eCRF.
- Results in persistent or significant disability/incapacity: An AE is incapacitating or disabling if it results in a substantial and/or permanent disruption of the participant's ability to carry out normal life functions.
- Results in a congenital anomaly/birth defect.
- Is another medically important event

Other important medical events that may not be immediately life threatening or result in death or hospitalization, based upon appropriate medical judgement, are considered SAEs if they are thought to jeopardize the participant and/or require medical or surgical intervention to prevent one of the outcomes defining an SAE. SAEs are critically important for the identification of significant safety problems; therefore, it is important to consider both the Investigator's and Sponsor's assessment.

The incidence of all serious TEAEs will be presented by SOC and preferred term for each treatment of event. A data listing of serious adverse events (SAEs) will also be presented.

**18.2.5 TEAEs leading to early withdrawal from study**

TEAEs leading to early withdrawal from study are defined as, in the Investigator's judgement, continued participation would pose unacceptable risk to the participant or to the integrity of the study data.

The incidence of all serious TEAEs leading to early withdrawal will be presented by SOC and preferred term for each treatment of event. A data listing of AEs leading to early withdrawal from study will be presented.

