8.4. Treatment Modifications and Discontinuations

Dose reductions and adjustments are not permitted; any dose reductions and adjustments that occur will be recorded and considered protocol deviations.

Delays and omissions of study treatment administration because of medical or nonmedical reasons are not permitted. All delays and omissions of study treatment that occur during the study will be recorded and considered protocol deviations.

A participant may be discontinued from the study at any time for reasons including, but not limited to, the following:

- AE and/or SAEs in the judgment of the Investigator that may prevent the participant from continuing participation in the study.
- Participant withdrawal of consent (at any time, a participant's participation in the study may be terminated at their request).
- On the basis of the Investigator's clinical judgment.
- General or specific changes in the participant's condition that render them ineligible for further treatment according to the inclusion/exclusion criteria.
- Participant fails to adhere to the protocol requirements (e.g., study treatment noncompliance).
- Lost to follow up: the participant stopped coming for visits and study personnel were unable to contact the participant.

Note: In cases in which the participant is deemed lost to follow up, prior to this designation, the Investigator (or designee) must make every effort to make contact with the participant (e.g., telephone calls, certified letter to the participant's last known mailing address, or local equivalent methods, and efforts to reach the participant's emergency contact). The site will make 3 attempts to regain contact with the participant. These contact attempts must be documented in the participant's medical records.

Any participant who discontinues from the study will be asked to return to the clinic for an EOS visit that includes the assessments as shown in the schedule of assessments ([Table 3](#)). The reason and date for the participant's discontinuation from the study must be recorded in the eCRF.

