**18.2.6 TEAEs leading to death**

Treatment-emergent adverse events (TEAEs) leading to death are defined as TEAEs where there is a reasonable possibility of death occurring due to the IP.

The incidence of all TEAEs leading to death will be presented by SOC and preferred term for each treatment of event. A data listing of all AEs for deceased participants will be presented.

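### The SAP's table of TEAEs leading to withdrawal counts only serious events, and its definition of TEAEs leading to death turns on causality instead of fatal outcome

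*SAP*

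**What the plan says.** **Withdrawal (SAP 18.2.5).** The section is headed for TEAEs leading to early withdrawal from the study. It defines them by the investigator's judgement that "continued participation would pose unacceptable risk to the participant or to the integrity of the study data". Two outputs follow. The table: "The incidence of all serious TEAEs leading to early withdrawal will be presented by SOC and preferred term for each treatment of event". The listing: "A data listing of AEs leading to early withdrawal from study will be presented".

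Protocol 8.4 gives as a reason for discontinuation "AE and/or SAEs in the judgment of the Investigator that may prevent the participant from continuing participation in the study".

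**Death (SAP 18.2.6).** TEAEs leading to death are "defined as TEAEs where there is a reasonable possibility of death occurring due to the IP". The table: "The incidence of all TEAEs leading to death will be presented by SOC and preferred term for each treatment of event". The listing: "A data listing of all AEs for deceased participants will be presented".

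*Treatment of event* is defined in SAP 18.2.3 as the last product received before the AE began. It is how these tables assign an event to a product in the crossover.

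**The concern.** Withdrawal because of an AE is a standard tolerability summary. Safety of NKF-INS(A) is a secondary objective, and Protocol 4.1 states that this is the product's first clinical study. Protocol 4.2 names hypoglycemia and allergic reactions among the known effects of insulin aspart products. Such events can be non-serious and still end a participant's involvement. If the table follows its own sentence, a withdrawal of that kind is not counted under the product that preceded it.

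The death definition has a different fault. It builds a relatedness judgement into what should be a classification by outcome. A table whose title promises all fatal TEAEs would show only those considered possibly due to the study product.

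**Working it through.** There is no figure to reproduce. The check sets the relevant texts side by side.

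**Step 1: is 18.2.5 consistent with itself?**

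| Element | Limited to serious events? |
|---|---|
| Heading | No |
| Definition | No |
| Incidence table | **Yes** |
| Listing | No |
| Protocol 8.4, reason for discontinuation | No; non-serious and serious AEs both qualify |

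The table sentence is the only element that restricts. In symbols: table count = (TEAEs leading to withdrawal) − (non-serious TEAEs leading to withdrawal). The table is right if the second term is zero and too low otherwise.

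**Step 2: does another planned output give the missing count by product?**

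- SAP 18.2.1 and 18.2.2 tabulate all TEAEs by treatment of event. A non-serious event that led to withdrawal is in those tables, but not marked as having done so.
- SAP 12.2 summarizes disposition and withdrawals. The default stratification in SAP section 8 is by randomized sequence. Every sequence contains all three products, so a count by sequence alone does not attribute a withdrawal to one of them.
- The overall summary in SAP 18.2 counts participants in the event categories that the sub-sections describe. It is not stated whether the withdrawal category there follows the unrestricted definition or the restricted table sentence. The text on that summary does not say that it is broken down by product.
- Protocol 14.5 lists no withdrawal table.
- The 18.2.5 listing is complete but promises no incidence.

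The 18.2.5 table is therefore the only planned incidence table that clearly links AE withdrawal to product.

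**Step 3: does the 18.2.6 definition match its neighbours?**

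| Place | Criterion | Requires relation to the product? |
|---|---|---|
| SAP 18.2.4, serious criteria | The event resulted in death | No |
| SAP 18.2.2, Grade 5 | Death related to the AE | No |
| SAP 18.2.6, definition and table | Reasonable possibility of death due to the product | **Yes** |
| SAP 18.2.6, listing | Any AE of a deceased participant | No |

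A fatal TEAE judged unrelated meets the first, second and fourth rows but not the third. Table and listing within 18.2.6 would then disagree. Read literally, the third row also does not say that death occurred, so a non-fatal event could qualify. The wording can therefore err in both directions.

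**Step 4: where would omitted events still be seen?** A non-serious TEAE leading to withdrawal would be in the 18.2.1 and 18.2.2 tables, the 18.2.5 listing and the full AE listing in 18.2, which includes action taken and outcome. An unrelated fatal TEAE would be in the 18.2.1 table, the 18.2.2 table as Grade 5, the 18.2.4 serious TEAE table and the listings.

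**The case against.** The strongest reply is that nothing is hidden. Every event stays in the all-TEAE and severity tables by treatment of event, and the withdrawal listing is unrestricted. With 54 participants planned, that listing can be counted by hand. An unrelated fatal TEAE would reach the serious TEAE table and the Grade 5 row, and deaths are unlikely in a single-dose healthy-volunteer study. The word *serious* may simply have been carried over from the similar sentence in 18.2.4. The table shells are in a separate document and may not repeat it. Protocol 14.5 asks for neither table, so no protocol commitment is broken.

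Most of this stands, and it limits the consequence. It does not make the table sentence correct. The tables that retain a non-serious event do not show that it caused withdrawal. A carry-over is an inference, and the written sentence is what a programmer would follow.

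Three stronger readings are tempting but not supported:

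- *That withdrawals caused by one product could go unseen.* The listings and the by-product tables of all TEAEs rule this out. What is lost is one summary count.
- *That the gap between 54 enrolled and at least 36 evaluable measures the problem.* That gap (54 − 36 = 18; 18/54 = 33%) covers non-evaluability from any cause. The stated dropout assumption is 20%, also without regard to cause. Neither is an AE-withdrawal rate.
- *That the overall AE summary must inherit the restriction.* It may, but its text can equally be read as using the unrestricted definition.

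**Conclusion.** Both sentences are wrong as written. The 18.2.5 table contradicts its own heading, definition and listing, and would omit every non-serious TEAE that leads to withdrawal. The 18.2.6 definition would exclude any fatal TEAE judged unrelated to the product and does not clearly require a death.

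The under-count is conditional. It needs at least one non-serious AE withdrawal, or at least one fatal TEAE judged unrelated. The first is plausible and carries the weight of the point; the second is unlikely here. The documents give no AE-withdrawal rate, so no magnitude can be stated. The effect is confined to safety summaries, and the primary PK and PD comparisons do not depend on either table.

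The conclusion assumes that the tables are programmed as the SAP text reads, since the output templates are not among the documents.

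**What to change.** 1. In SAP 18.2.5, delete *serious* from the table sentence, so that every TEAE leading to early withdrawal is tabulated by SOC, preferred term and treatment of event. Serious events can be shown as a subset if wanted.
2. In SAP 18.2.6, define the category as TEAEs with a fatal outcome regardless of relationship to study product, and show relationship in the table.
3. Align the table shells with both sentences, and state in SAP 18.2 that the overall summary uses the same two definitions.

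The cost is two corrected SAP sentences, one clarifying sentence and a check of the shells. No new data are needed. The 18.2.5 listing already requires that AEs leading to withdrawal be identified. The AE listing in SAP 18.2 already carries relationship, action taken and outcome. Protocol 7.4 and 8.4 already require the reason for discontinuation in the eCRF.

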**18.2.6 TEAEs leading to death**

Treatment-emergent adverse events (TEAEs) leading to death are defined as TEAEs where there is a reasonable possibility of death occurring due to the IP.

The incidence of all TEAEs leading to death will be presented by SOC and preferred term for each treatment of event. A data listing of all AEs for deceased participants will be presented.

## 19. Safety laboratory tests

All summaries for Safety laboratory tests will be based on the SAF population, unless otherwise specified. Data listings will be based on the SAF population.

### 19.1 Variables and derivations

For safety laboratory data, baseline will be defined as the last observation made prior to the first administration of IP.

The following laboratory tests (haematology, clinical chemistry and urinalysis) to be included in the analysis:

#### 19.1.1 Hematology

Ethylenediaminetetraacetic acid (EDTA) tubes:

- Full and differential blood count,
- White blood cell (WBC) count,
- Red blood cell (RBC) count,
- Hemoglobin (Hb),
- Hematocrit (HCT),
- Mean corpuscular volume (MCV),
- Mean corpuscular hemoglobin (MCH),
- Mean corpuscular hemoglobin concentration (MCHC),
- Absolute differential count (neutrophils, lymphocytes, monocytes, eosinophils, and basophils) and
- Platelets

#### 19.1.2 Clinical Chemistry

Serum separator tubes (SST):

- Potassium,
- Sodium,
- Urea,
- Chloride,
- Phosphorus,
- Creatinine,
- Calcium,
- Albumin,
- Total and direct bilirubin,
- Creatine kinase,
- Alkaline phosphates (ALP),
- Gamma glutamyl transferase (GGT),
- Aspartate aminotransferase (AST),
- Alanine aminotransferase (ALT),
- Lactate dehydrogenase,
- Total cholesterol,
- Triglycerides,
- Glucose

#### 19.1.3 Blood coagulation tests

Citrated tubes:

- Prothrombin time (PT),
- Activated partial thromboplastin time (aPTT)
- International normalized ratio (INR)

#### 19.1.4 Urinalysis

- Appearance,
- Glucose,

- bilirubin,
- ketone,
- specific gravity,
- Blood,
- pH,
- protein,
- urobilinogen,
- nitrite
- leucocytes.

Abnormal urinalysis results may be repeated at the discretion of the investigator.

Quantitative laboratory measurements reported as “< X.XX”, i.e. below limit of quantitation, or “> X.XX”, i.e. above the upper limit of quantification, will be converted to X.XX for quantitative summaries, but will be presented as recorded, i.e. as “< X.XX” or “> X.XX” in the data listings.

## 19.2 Analysis

The SAF population alone will be used to analyse safety laboratory data.

Summaries of haematology, clinical chemistry, blood coagulation and urinalysis laboratory tests for each treatment sequence, by visit and by time point, will include descriptive statistics of the following:

- Actual and change from baseline (for quantitative measurements)
- Frequencies and percentages (n and %) (for qualitative measurements)

Quantitative laboratory measurements will be compared with the relevant laboratory reference ranges and categorised as:

- Low: Below the lower limit of the laboratory reference range
- Normal: Within the laboratory reference range (upper and lower limit included)
- High: Above the upper limit of the laboratory reference range

These categorizations will only be presented in data listings. Other laboratory results (apart from haematology, clinical chemistry and urinalysis laboratory tests), e.g. urine microscopy, will be listed. A separate listing containing clinically significant laboratory results will be presented.

## 20. Vital signs

All summaries, and data listings, for vital signs will be based on the SAF population, unless otherwise specified.

Vital signs will be measured after the participant has been resting quietly in a seated position for at least 5 minutes. Vital sign measurements will be repeated if clinically significant abnormal or machine/equipment errors occur. Out-of-range blood pressure, respiratory rate, or heart rate measurements may be repeated at the Investigator's discretion. Any confirmed, clinically significant abnormal vital sign measurements must be recorded as AEs.

### 20.1 Variables and derivations

For vital signs, baseline is defined as the last observation made prior to the first administration of IP.

---

The following vital signs will be reported for this study:

- Systolic blood pressure (mmHg)
- Diastolic blood pressure (mmHg)
- Heart rate (bpm)
- Body temperature (°C) (temporal or ear temperature measurements).
- Respiratory rate (breaths/min)

## 20.2 Analysis

The following summaries will be provided for vital signs data for each treatment sequence, by visit:

- Actual and change from baseline by visit
- Descriptive statistics (n, arithmetic mean, SD, minimum, median, maximum) for absolute values.

Abnormal quantitative vital signs will be identified in accordance with the following predefined abnormal criteria:

- Systolic blood pressure: 90 to 140 mmHg
- Diastolic blood pressure: 50 to 90 mmHg
- Heart rate: 40 to 100 bpm
- Body temperature: 35.5 to 37.5 °C

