12.1. Vital Signs

Vital signs (heart rate, respiratory rate, systolic and diastolic blood pressure, and temporal or ear temperature measurements) will be evaluated at the timepoints indicated in the schedule of assessments ([Table 3](#)). All vital signs will be measured after the participant has been resting in a supine position for at least 5 minutes. Height (without shoes) will be recorded at screening. Weight will be recorded at screening and on Day -1.

Vital sign measurements will be repeated if clinically significant abnormal or machine/equipment errors occur. Out-of-range blood pressure, respiratory rate, or heart rate measurements will be repeated at the Investigator's discretion. Any confirmed, clinically significant abnormal vital sign measurements must be recorded as AEs.

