### 21.2 Electrocardiograms

A 12-lead, resting ECG will be obtained at the timepoints indicated in the schedule of assessments (Section 4.2; Protocol NKF-INS(A)-101, Version 2.0, dated 06-May-24). ECG should always be performed after the participant has been resting in a supine position for at least 5 minutes.

The frequency of abnormalities (e.g., heart rate, PR interval, QRS complex, and QTcF [Fridericia's corrected QT]) will be summarized by treatment group and scheduled visits using counts and percentages.

---

An assessment of normal, abnormal clinically significant, or abnormal not clinically significant will be recorded; if the ECG is considered abnormal, the abnormality will be documented in the eCRF. ECGs may be repeated if clinically significant abnormalities are observed, or artifacts are present. Any confirmed, clinically significant abnormal ECG findings must be recorded as AEs.

Participant ECG status (normal, abnormal clinically significant, or abnormal not clinically significant) may be summarized for each scheduled ECG and shifts from screening may be tabulated. Raw data and derivations will also be presented as a listing for the SAF population. Data will be analysed as outlined in ICH E14.

Abnormal ECG values will be identified in accordance with the following predefined normal criteria:

- PR Interval: 120 to 220 (msec)
- QRS Duration: < 120 (msec)
- Heart rate: 50 to 100 (bpm)
- QTc Interval: 350 to 450 (msec)
- For the QT, QTcF parameters, the following categorisations will be done:
  - $x \leq 450$  ms (considered as normal range)
  - $450 < x \leq 480$  ms
  - $480 < x \leq 500$  ms
  - $x > 500$  ms

and for change from baseline:

- $x \leq 30$  ms (considered as normal range)
- $30 < x \leq 60$  ms
- $x > 60$  ms
- For the PR parameter, the following categorisations will be done:
  - $x < 120$  ms
  - $120 \leq x \leq 220$  ms (considered as normal range)
  - $x > 220$  ms
- For heart rate, the following categorisations will be done:
  - $x < 50$  bpm
  - $50 \leq x \leq 100$  bpm (considered as normal range)
  - $x > 100$  bpm

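### The SAP labels normal vital-sign ranges as abnormal criteria and applies QTc-type cut-offs to uncorrected QT; both rules need rewording before the safety outputs are programmed

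*SAP*

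**What the plan says.** **Vital signs.** SAP 20.2 introduces its limits with "Abnormal quantitative vital signs will be identified in accordance with the following predefined abnormal criteria". It then lists "Systolic blood pressure: 90 to 140 mmHg", "Diastolic blood pressure: 50 to 90 mmHg", "Heart rate: 40 to 100 bpm" and a temperature range of 35.5 to 37.5 °C.

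**ECG.** SAP 21.2 uses the same sentence form for ECG values but calls the limits normal, not abnormal. Its interval limit of 350 to 450 ms is stated for QTc, and its heart-rate limits are 50 to 100 bpm. It then adds: "For the QT, QTcF parameters, the following categorisations will be done". The categories are up to 450, above 450 to 480, above 480 to 500, and above 500 ms. Change from baseline is cut at 30 and 60 ms. The lowest category is marked as normal in each case.

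**Protocol.** Section 14.5 asks, for laboratory data and vital signs, for counts of participants outside normal limits at each timepoint. The synopsis says that potentially clinically significant laboratory, vital-sign and ECG values will be flagged and summarised.

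**Posture.** SAP 20 says "Vital signs will be measured after the participant has been resting quietly in a seated position for at least 5 minutes". Protocol 12.1 says "All vital signs will be measured after the participant has been resting in a supine position for at least 5 minutes", and footnote 9 to protocol Table 3 also specifies supine.

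**The concern.** A SAP is what the programmer codes from. If the vital-sign rule is coded as written, each flag comes out the wrong way round: ordinary readings are listed as abnormal and the readings that matter are not.

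The QT problem is of a different kind. Raw QT shortens as heart rate rises and lengthens as it falls, which is why a corrected interval is used. A fixed millisecond cut-off on raw QT therefore partly classifies heart rate. A recording can be normal on one row of the table and prolonged on the next, and neither row would explain why.

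Safety is a secondary objective, with vital signs and ECG among its endpoints, and protocol 4.2 says the product's safety has not been evaluated in humans. These outputs should be right even though they are descriptive.

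**Working it through.** The plan states no figure to reproduce on this point. The checks are a literal application of the vital-sign rule, a conversion between QT and QTcF, and a comparison of passages.

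**1. Vital-sign rule (SAP 20.2).** Each limit was applied as worded (inside the range is abnormal) and as a normal range (outside is abnormal).

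| Reading | As worded | As a normal range |
|---|---|---|
| Systolic 120 / 180 mmHg | abnormal / not flagged | not flagged / abnormal |
| Diastolic 75 / 110 mmHg | abnormal / not flagged | not flagged / abnormal |
| Heart rate 65 / 130 bpm | abnormal / not flagged | not flagged / abnormal |
| Temperature 36.6 / 39.0 °C | abnormal / not flagged | not flagged / abnormal |

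Every flag reverses. Only the right-hand column agrees with the ECG wording in SAP 21.2 and with the counts promised in protocol 14.5.

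**2. QT categories (SAP 21.2).** The documents name Fridericia's correction but do not print it. The standard form is assumed: QTcF = QT / (60/HR)^(1/3). The heart rates used lie within 50 to 100 bpm, the range SAP 21.2 treats as normal.

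| HR (bpm) | (60/HR)^(1/3) | QTcF when raw QT = 450 ms | Raw QT when QTcF = 450 ms |
|---|---|---|---|
| 50 | 1.0627 | 423.5 | 478.2 |
| 60 | 1.0000 | 450.0 | 450.0 |
| 75 | 0.9283 | 484.7 | 417.7 |
| 100 | 0.8434 | 533.5 | 379.5 |

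- At 50 bpm, a raw QT of 478 ms falls in the 450–480 category, while the QTcF of 450 ms is normal.
- At 100 bpm, a raw QT of 450 ms is normal, while the QTcF of 533.5 ms falls in the category above 500.

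The change categories have the same defect. Hold QTcF at 450 ms, so that its true change is zero:

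- If heart rate falls from 75 to 60 bpm, raw QT changes by 450.0 − 417.7 = 32.3 ms, which is in the 30–60 category.
- If it falls from 100 to 60 bpm, raw QT changes by 450.0 − 379.5 = 70.5 ms, which is in the category above 60.

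**3. Secondary items.** With the vital-sign limits read as normal ranges, a rate of 40 to 49 bpm is normal under SAP 20.2 and abnormal under SAP 21.2. The upper limits agree at 100 bpm. The posture sentences in SAP 20 and protocol 12.1 cannot both describe how the readings were taken.

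**The case against.** The strongest reply is that the vital-sign problem is one wrong word whose meaning is plain. The ECG sentence and protocol 14.5 both show the intended direction, and neither of the two summaries listed in SAP 20.2 uses the flag. This stands as to intent: a reader might infer that the report will contain reversed flags, and the documents do not support that. It does not remove the error, because the sentence is the operative rule for a flag that the protocol expects to see.

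On QT, QTcF is categorised by the same cut-offs, so the corrected result would appear beside the raw one, and the raw row would be labelled as QT. ECGs are scheduled only at screening and end of study, so they give no per-product comparison in this crossover. SAP 21 also opens by confining its assessments to listings, while 21.2 describes summaries, so how far the categories reach the tables is unsettled. All of this limits the harm, but none of it makes the cut-offs meaningful for raw QT. A reader might want a percentage of men misclassified. The documents give neither a QTcF nor a heart-rate distribution, so no such figure is supported.

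The 40 and 50 bpm limits belong to two different assessments and may be deliberate. Calling them a contradiction goes too far; what can be said is that the difference is unexplained. A reader might also infer that seated prevails, since protocol 14 gives the SAP precedence. That clause concerns analysis variables and methods, and a SAP cannot change how a site took its readings.

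**Conclusion.** Two descriptive safety rules in the SAP are wrong as written. The vital-sign rule is reversed by its label for all four listed measures, although the intended direction can be recovered from elsewhere in the documents. The QT rule applies fixed cut-offs to an uncorrected interval. Across the SAP's own normal heart-rate range, its 450 ms boundary corresponds to QTcF values from 423.5 to 533.5 ms, so it overstates prolongation at slow rates and hides it at fast ones. That result rests only on the standard Fridericia formula.

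The posture mismatch is a real conflict between the documents, but it is about measurement and is not a flagging rule. The two lower heart-rate limits are an unexplained difference. Which limits are clinically right is not judged here.

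A reader might infer that the trial's conclusions are at risk, but the documents do not support this. The PK/PD equivalence analyses, power and sample size do not use these rules. Adverse events depend on the investigator's judgement of clinical significance (protocol 12.1 and 12.3), not on the flags.

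**What to change.** - **SAP 20.2:** call the limits normal criteria, and state that values below the lower or above the upper limit are flagged.
- **SAP 21.2:** restrict the 450/480/500 ms and 30/60 ms categories to QTcF. Present uncorrected QT in listings only, without these categories.
- **SAP 20 against protocol 12.1 and Table 3 footnote 9:** reconcile the posture statements, so that the analysis plan describes the readings as they were taken.
- **SAP 20.2 against 21.2:** confirm that the different lower heart-rate limits for vital signs and ECG are intended, with a short reason, or reconcile them.

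The cost is SAP wording only, if done before programming. No data collection, sample size or primary analysis changes.
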